Neuromuscular Intervention Targeted to Mechanisms of ACL Load in Athletes

NCT03190889

October 28, 2024

IRB Minimal Risk Protocol Template

Note: If this study establishes a human specimen repository (biobank) for research purposes, do not use this template. Use the Mayo Clinic Human Specimen Repository Protocol Template found on the IRB home page under Forms and Procedures at <http://intranet.mayo.edu/charlie/irb/>

First-time Use: Use this template to describe your study for a new IRB submission.

1. Complete the questions that apply to your study.
2. Save an electronic copy of this protocol for future revisions.
3. When completing your IRBe application, you will be asked to upload this document to the protocol section.

Modification: To modify this document after your study has been approved:

1. Open your study in IRBe. Click on the study 'Documents' tab and select the most recent version of the protocol. Save it to your files.
2. Open the saved document and activate "Track Changes".
3. Revise the protocol template to reflect the modification points , save the template to your files
4. Create an IRBe Modification for the study and upload the revised protocol template.

General Study Information

Principal Investigator: [name]

Study Title: Neuromuscular Intervention Targeted to Mechanisms of ACL Load in Athletes

Protocol version number and date: version 4.5, 08/27/2020

Research Question and Aims

Specific Aims and Hypotheses

Aim 1. Determine if prospective measures can identify patient risk profiles for second ACL injury by separation of patient groups using biomechanical and clinical risk factors.

Hypothesis 1A: Landing biomechanics (vGRF, frontal and transverse plane hip moments, frontal plane knee and hip motion, and asymmetrical sagittal plane knee moments), quadriceps and hamstrings strength and single leg postural stability will effectively identify discrete patient risk profiles for second injury based on knee abduction (KAA) and hip adduction angles (HAA), surrogates for ACL injury.

Aim 2. Determine the effects of differential rehabilitation, including the impact on biomechanical measures of ACL injury risk and return to sport readiness after ACLR.

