Factors that contribute to primary ACL injury risk provide an important window into the underlying deficits that may persist after ACL injury and reconstruction. Age and activity level are significant factors, as young active individuals are the most likely cohort to sustain a second ACL rupture.^{6, 27, 30, 41} Surgical factors include decreased graft size,^{42, 43} use of allograft tissue,⁴⁴ vertical graft position,⁴⁵⁻⁴⁷ and a lax graft.^{45, 48} Anatomical risk factors may also contribute to ACL injury risk and include an increase in the posterior-inferior lateral tibial plateau slope and decreased notch width.⁴⁹ Genetic factors also likely play a role. While it is encouraging that so many potential factors have been identified which may contribute to second ACL injury risk, none of these factors can be modified through non-surgical intervention. Modifiable biomechanical and neuromuscular measures associated with second ACL injury have been identified. Previous work by our laboratory included a prospective clinical trial,⁵⁶ athletes who had undergone ACLR underwent testing before a return to pivoting and cutting sports. Thirteen athletes sustained a subsequent injury.¹⁵ Specific injury predictive parameters identified during testing included a net internal rotation moment of the uninvolved hip, an increase in total frontal plane knee movement, greater asymmetry in internal knee extensor moment at initial contact, and deficits in single-leg postural stability of the involved limb.¹⁵ These parameters predicted second injury in this population with excellent sensitivity (0.92) and specificity (0.88).

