Overall Strategy. This is a prospective, randomized, repeated measures single- blind clinical trial. The purposes of this study are to 1) stratify patient risk for second ACL injury, and 2) determine the effects of differential treatment intervention, including targeted neuromuscular training (TNMT), home program only (HOME) and standard clinical (STAN) training, on clinical, biomechanical, and neuromuscular performance measures associated with an increased secondary ACL injury risk. At this time there is no evidence to support one intervention as either superior or inferior to the other interventions proposed in this study. After the initial ACL injury and study enrollment, all patients will participate in standardized pre-operative rehabilitation. They will then undergo surgery by a fellowship-trained sports medicine surgeon at Mayo Clinic, Rochester, MN. Data for Aim 1 will be obtained from biomechanical, neuromuscular and clinical testing performed during Pre-Testing. Data for Aim 2 and the Exploratory Aim will be obtained from biomechanical and clinical test results obtained from Pre- and Post-Testing time points.

Common Rehabilitation. All study participants will follow the same rehabilitation guidelines before and immediately after surgery, until they are cleared by their attending surgeon to return to full participation in sports. After clearance, they will be randomized into the differential treatment groups. Entry into this phase is criteria-based, and represents the standards identified in the literature for entry into the final phase of rehabilitation. These criteria include: symmetrical knee range of motion; minimal or no pain and knee effusion; quadriceps strength $\geq 80\%$ compared to contralateral limb (180°/sec and 300°/sec); self-report of function $\geq 80\%$; limb symmetry index during single leg hop for distance $\geq 80\%$. Both pre- and postoperative rehabilitation protocols are a composite of previously published, evidence-based protocols from expert researchers and clinicians.⁶⁵⁻⁶⁷

Differential Rehabilitation. Once study participants are cleared for full participation in sports, they will be randomized into one of three groups for differential treatment. This will include HOME, STAN and TNMT

groups. If patient lives at a distance from Mayo Clinic and cannot participate in the weekly training but is able to come to both testing session they will be randomized into the HOME and STAN programs.

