Check 'None' when none of the identifiers listed above will be recorded, maintained, or shared during the conduct of this study. (exempt category 4)	 None	 None

Data Analysis

Power analyses and study endpoints are not required for minimal risk research, pilot or feasibility studies.

No statistical information. *If checked, please explain:*

Power Statement:

We expect that the minimal clinically significant effect size of TNMT on knee biomechanics is 0.17 or above. Using an a priori power analysis based on repeated measures ANOVA, we expect that to achieve 80% power with $\alpha = 0.05$, this study will require a final accrual of 87 subjects. This assumes a correlation coefficient of 0.3 among the repeated measures, which is likely conservative. Thus, an accrual of 116 (with an estimated 30% dropout rate) subjects will be sufficient to determine if a clinically significant reduction in unininvolved limb transverse plane hip net moment impulse, frontal plane knee joint ROM, initial contact sagittal plane knee moment asymmetry, and deficits of involved limb postural stability has occurred as a result of TNMT. This sample size provides adequate power for all variables of interest for Aims 1 and 2. Mayo Clinic averages more than 120 ACLR per year in the Minneapolis/Rochester region on individuals under age 25. Thus, the available patient pool is more than adequate to meet study requirements.

Data Analysis Plan:

Aim 1: We will utilize normal mixture based clustering analysis⁷⁰ to identify groups with distinguished risks based on a priori covariates (i.e., demographics and biomechanical variables). Our previous work used a similar approach to effectively cluster subjects into three distinct risk groups. We intend to confirm disparate risk for injury by assessment of the magnitude of differences across groups using knee and hip abduction angles, surrogates for ACL injury.

The normal mixture model approach works by assuming the density of the covariates for a subject x , can be described as:

$$f(x) = \sum_{k=1}^K \pi_k \phi(x; \mu_k, \Sigma_k),$$

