where (i) K is the number of mixture components (groups), (ii) π_k is the unconditional probability that a subject fall into the k th group, and (iii) $\phi(\cdot; \mu, \Sigma)$ is the multivariate normal density with mean μ and covariance Σ . Estimates of the parameters, π_k, μ_k, Σ_k , are typically obtained using maximum likelihood. The number of groups is most commonly chosen to optimize the Bayesian Information Criterion (BIC). Often assumptions such as a common covariance matrix for all k , or common shape (i.e., correlation) matrix, are made to make estimation feasible, depending on the size of data, and these decisions are also commonly made on the basis of BIC. In this work we intend to assume a common Σ , and assess the validity of this assumption via model diagnostics. Once parameter estimates are obtained, clustering is performed by calculating the probability of group membership m for a given subject, conditional on his/her covariate values, i.e.,

$$P(m = k | x) = \frac{\pi_k \phi(x; \mu_k, \Sigma_k)}{\sum_{l=1}^K \pi_l \phi(x; \mu_l, \Sigma_l)}.$$

The subject will then be assigned to the group k that results in the largest conditional group membership probability $P(m = k | x)$. This approach has been shown to perform very well in the presence of a large number of variables with the inclusion of a variable selection mechanism.^{71, 72} We will leverage such an approach in our analysis to identify a reduced set of biomechanical variables that most informatively differentiate the subjects.

Aim 2:

Aim 2 will utilize a prospective, single blind, randomized clinical trial design. Subjects from Aim 1 will comprise the study sample. Subjects will undergo testing twice.

We will use a repeated-measures ANOVA model with between-subjects factors that include interactions, to determine the effect of TNMT compared to HOME or STAN treatment on clinical performance after ACLR. Specifically, for a response of interest y , e.g., hip abductor strength, for the i^{th} subject in the k^{th} treatment group, with $l = 0$ indicating before intervention and $l = 1$ indicating after,

$$y_{ikl} = \alpha + \delta_l + (\gamma\delta)_{kl} + \tau_{i(k)} + \epsilon_{ikl}$$

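### Aim 1 plans to confirm that clusters differ in injury risk from surrogate angles taken at the same baseline testing, and no planned analysis compares clusters on second injury

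*Combined protocol and SAP*

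**What the plan says.** All references are to the combined protocol and SAP.

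- **Target.** Aim 1 concerns risk profiles for second ACL injury. Hypothesis 1A lists the profiling measures, among them "frontal plane knee and hip motion, and asymmetrical sagittal plane knee moments", and says that the profiles are "based on knee abduction (KAA) and hip adduction angles (HAA), surrogates for ACL injury".
- **Inputs.** The Data Analysis Plan for Aim 1 forms groups by a normal mixture model, "based on a priori covariates (i.e., demographics and biomechanical variables" being the only description of what goes in. A variable-selection step will then "identify a reduced set of biomechanical variables that most informatively differentiate the subjects".
- **Check.** The same section states: "We intend to confirm disparate risk for injury by assessment of the magnitude of differences across groups using knee and hip abduction angles". The sentence ends by calling the angles surrogates for ACL injury.
- **Timing.** Overall Strategy: "Data for Aim 1 will be obtained from biomechanical, neuromuscular and clinical testing performed during Pre-Testing". For the rest: "Data for Aim 2 and the Exploratory Aim will be obtained from biomechanical and clinical test results obtained from Pre- and Post-Testing time points".
- **Injury data.** Tracking plans monthly injury surveys for two years after training and yearly follow-up for four more, six years in all. Endpoints lists second injury as the secondary endpoint.

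**The concern.** The sentence on the check promises a conclusion about injury risk, but the comparison behind it contains no injuries. It sets one group of baseline measurements against another from the same testing. Followed as written, Aim 1 could report that its clusters have been shown to differ in second-injury risk when only a surrogate has been compared.

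The label is meant to be carried further. The Background describes the Exploratory Aim as a first step in turning the group algorithm into individual risk categories. It also hopes to learn whether less intensive programmes suffice for patients at reduced risk. A reader of the Aim 1 report would need to know whether high and low risk were ever set against injuries.

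A second uncertainty sits underneath. If the angles used as the check also help to form the clusters, some difference between clusters on those angles is built in.

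**Working it through.** The plan gives no figure for the Aim 1 check, so there is none to reproduce. The check is mainly a reading of the passages, followed by short arithmetic on what an injury comparison could show.

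**1. Does any analysis link cluster to second injury?**
- Aim 1 analysis: mixture clustering, then the angle comparison. No injury term.
- Aim 2 analysis: pre-to-post change by treatment group. No injury term.
- Exploratory Aim: concerns second-injury risk, but its stated data are Pre- and Post-Testing results and it has no analysis section.
- Tracking and Endpoints: injuries are collected and named, with no model, test or table attached.

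So none does.

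**2. Are the check angles clustering inputs?** Hypothesis 1A puts frontal plane knee and hip motion among the profiling measures and names the knee abduction and hip adduction angles as the yardstick. The Aim 1 analysis describes the inputs only in general terms and excludes nothing, either there or at variable selection. The knee input might be a different quantity: the Background cites "an increase in total frontal plane knee movement" as a predictor, and the Power Statement refers to frontal plane knee joint range of motion. Overlap is possible but not stated.

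**3. What would a difference in angle imply for injury risk?** That depends on the odds ratio (OR) for second injury per SD of the angle, which the documents do not give. Suppose the highest and lowest clusters differ by 1 SD. Put their risks at logit(base) ± ln(OR)/2, with the base rates of 6% and 29% from the Background:

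| Base rate | Assumed OR per SD | Higher risk | Lower risk | Risk ratio |
|---|---|---|---|---|
| 6% | 1.0 | 0.060 | 0.060 | 1.00 |
| 6% | 1.5 | 0.073 | 0.050 | 1.46 |
| 6% | 2.0 | 0.083 | 0.043 | 1.92 |
| 29% | 1.0 | 0.290 | 0.290 | 1.00 |
| 29% | 1.5 | 0.333 | 0.250 | 1.33 |
| 29% | 2.0 | 0.366 | 0.224 | 1.63 |

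Ratios use unrounded risks. The same angle gap fits no difference in injury risk or nearly a doubling.

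**4. How many injuries could a table by cluster hold?** Expected events = rate × N. The three values of N are the requirement in the Power Statement (87), 150 enrolled less 30% (150 × 0.70 = 105), and the final accrual stated under Target accrual (120).

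| N | At 6% | At 29% |
|---|---|---|
| 87 | 5.2 | 25.2 |
| 105 | 6.3 | 30.5 |
| 120 | 7.2 | 34.8 |

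The 6% covers two years from surgery, the 29% has no stated time frame, and the trial's injury surveys run six years from the end of training. The table therefore shows orders of magnitude only.

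**5. How precise would it be?** Assume three equal clusters. Exact (Clopper-Pearson) 95% intervals:

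| Injuries / cluster size | Observed | 95% interval |
|---|---|---|
| 2 / 29 | 6.9% | 0.8 to 22.8% |
| 8 / 29 | 27.6% | 12.7 to 47.2% |
| 2 / 40 | 5.0% | 0.6 to 16.9% |
| 12 / 40 | 30.0% | 16.6 to 46.5% |

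For at least 80% power (two-sided Fisher test, alpha 0.05), two clusters of 40 would need true risks of about 6% and 32% (power 82.5%). Two of 29 would need about 6% and 39% (82.2%). Only very large differences could be detected.

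**The case against.** The strongest reply is that Aim 1 is openly a surrogate-based aim. Both Hypothesis 1A and the analysis section call the angles surrogates, so nobody is misled about what is measured. This stands, and it limits the criticism to the conclusion drawn: naming a surrogate does not entitle the plan to confirm a difference in injury risk.

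The surrogate also has some support. The Background reports that frontal plane knee movement helped to predict second injury in a prior study. It did so jointly with three other measures and on 13 injuries, so the choice is plausible, but a comparison on injury is not made redundant.

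A third reply is that events will be too few and that the protocol template does not require endpoints for minimal-risk research. The sparseness is real and is why the table should be descriptive; it is also a reason not to claim confirmation. As to the template, the sponsor chose to state an analysis, an injury endpoint and a confirmatory conclusion, and these should agree.

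A reader might go further and infer that the check is circular, or probably so. The documents do not support that. They list the yardstick separately from the predictors and do not say whether the exact angles are inputs. How much overlap would matter depends on the cluster structure, the shape of the data and the variable selection, none of which can be fixed from the documents.

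A reader might also infer that patients will be treated according to an unvalidated label. Overall Strategy and Common Rehabilitation randomise after surgical clearance, and nothing assigns treatment by cluster.

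**Conclusion.** The concern holds in this form: the planned comparison can describe the clusters on surrogate measures, but it cannot confirm that second-injury risk differs, and no planned analysis tests or tabulates that. This holds whether or not the angles are clustering inputs. If they are, the comparison is also partly circular; the plan needs to say which.

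This should be corrected before analysis, but it does not invalidate the clustering. Nor does it show that the clusters will fail to differ in injury risk, or that the surrogate is poor; the documents leave both open.

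The central conclusion rests on the text alone. The risk ratios of 1.00 to 1.92 rest on assumed odds ratios and an assumed 1 SD gap. The event counts of about 5 to 35 borrow rates whose time frames do not match the follow-up, and the intervals assume equal clusters. The Aim 2 text mentions risk group in its primary inference while its equation has no such term; that is a separate point.

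**What to change.** 1. In the Aim 1 analysis, list the clustering inputs and name the check angles exactly (Hypothesis 1A says hip adduction, the analysis section hip abduction). Keep those specific angles out of both the clustering and the variable selection, or, if they stay in, do not use them as the check. Other frontal-plane inputs from Hypothesis 1A may remain.
2. Replace the statement about confirming injury risk with one saying that the angle comparison describes the clusters on surrogate measures.
3. Add a table of second-injury counts and incidence by cluster with exact confidence intervals, from the follow-up already planned. Label it descriptive, state the time window, and show randomised arm alongside, because treatment follows Pre-Testing.

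The cost is some wording and one table, with no new data. The drawback is imprecision. Splitting three clusters by three arms gives nine cells of roughly 10 to 13 subjects, with 0.06 × 10 = 0.6 to 0.29 × 13 = 3.8 expected injuries each. Arm counts should therefore be shown for context and not tested.

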6. One (1) static digitizing probe for creating calibration marker locations on hard-to-reach anatomical landmarks.
7. Two (2) Visual 3D motion analysis software licenses (C-motion inc., Germantown, MD)
8. Two (2) Microsoft Kinect 3D cameras (Microsoft Corp., Redmond, WA)
9. Two (2) Wii Balance boards (Nintendo of America, Inc., Redmond, WA)
10. Two HumacNORM isokinetic and isometric dynamometers with accompanying software (Figure FE2, CSMi, Stoughton, MA).
11. Two Humac balance devices with accompanying software (CSMi, Stoughton, MA).
12. One GNRB arthrometer (Genourob, Laval, France)
13. Two (2) complete Simi Aktisys marker-based and marker-less motion analysis systems with associated cameras, hardware, and software (Simi Reality Motion Systems GmbH, Unterschleissheim, Germany).
14. Thirteen (13) Dartfish Motion Pro Premium licenses with fourteen (14) associated cameras and necessary hardware split between Mayo Clinic Rochester and Mayo Clinic Square facilities (Dartfish USA, Inc., Alpharetta, GA).

Computer/Office

Adequate dedicated office space and computing capabilities already exists within the laboratories and clinical facilities to meet the needs of all personnel included in this project. Each listed clinical and laboratory space also has designated multimedia conference room space with teleconferencing capabilities. All key personnel have office space in both Minneapolis and Rochester SMCs.

(1a) This is a multisite study involving Mayo Clinic and non Mayo Clinic sites. *When checked, describe in detail the research procedures or activities that will be conducted by Mayo Clinic study staff.*

(1b) Mayo Clinic study staff will be engaged in research activity at a non Mayo Clinic site. *When checked, provide a detailed description of the activity that will be conducted by Mayo Clinic study staff.*

Subject Information

Target accrual: This study will enroll 150 subjects. Anticipating a 30% dropout rate, this will yield a final accrual of 120 subjects.

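### Aim 1 pre-sets one covariance matrix for all risk groups, with no named check or fallback; if the groups differ in spread, the number of groups can come out wrong

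*Combined protocol and SAP*

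**What the plan says.** The Aim 1 part of the Data Analysis Plan writes the normal mixture with a separate Σ for each group. It then notes that a common covariance matrix, or a common shape (correlation) matrix, is often assumed. Such assumptions "are made to make estimation feasible, depending on the size of data", and "these decisions are also commonly made on the basis of BIC". The next sentence states this study's choice: "In this work we intend to assume a common Σ , and assess the validity of this assumption via model diagnostics".

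No diagnostic is named. No threshold is given, and nothing is said about what follows if the check fails, including whether K would be chosen again. BIC is described as the usual way to choose K, but no rule or range of K is set for this study.

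On what is expected, the plan says: "Our previous work used a similar approach to effectively cluster subjects into three distinct risk groups". On how the groups would be checked: "We intend to confirm disparate risk for injury by assessment of the magnitude of differences across groups using knee and hip abduction angles". Variable selection is planned to "identify a reduced set of biomechanical variables that most informatively differentiate the subjects", but the number of variables is not given.

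**The concern.** A common Σ forces every group to have the same spread. If one group is truly wider, the model can fit it only by cutting it into narrower pieces, or by blurring it into its neighbour. The first gives too many groups, the second too few. Both can happen when every group is exactly normal, so checking the inputs for normality does not guard against them.

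The number of groups and their membership are the result of Aim 1: Hypothesis 1A is that the measures identify discrete risk profiles. The plan cites three groups from earlier work, so two groups cut into three would look like replication. The planned check on knee and hip angles need not expose this. Hypothesis 1A lists frontal plane knee and hip motion among the inputs, so pieces cut from one wide group may well differ on those angles.

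The Aim 2 text also counts the effect of risk group on intervention efficacy as part of its primary inference, although the displayed Aim 2 model has no risk-group term. If the text is followed, wrong groups would carry into Aim 2.

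**Working it through.** **The plan's own figure.** There is none to reproduce. The Power Statement says its sample size also serves Aim 1, but its 87 comes from a repeated-measures ANOVA. No separation, variance ratio or group share is given for the clustering.

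**Inputs from the documents.** 150 are enrolled, and Target accrual says: "Anticipating a 30% dropout rate, this will yield a final accrual of 120 subjects". Since 150 × 0.70 = 105, the check uses n = 105, 120 and 150.

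**Assumptions, not in the documents.** Two true normal groups; the group shares, separations, SD ratios and number of inputs shown below; K chosen by BIC over 1 to 4; no variable selection step.

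**Why a common Σ can split a group.** BIC = −2 log L + q ln n. With p inputs, the parameter counts are:
- common Σ: q = (K − 1) + Kp + p(p + 1)/2
- common shape with group-specific volume: K − 1 more than common Σ
- group-specific Σ: q = (K − 1) + Kp + Kp(p + 1)/2

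Take p = 4 and n = 120, so ln n = 4.79. Under a common Σ, a third group costs p + 1 = 5 parameters, or 5 × 4.79 = 23.9 BIC units. Staying at two groups and allowing different volumes costs one parameter, or 4.8 units. If only a common Σ is fitted, BIC never sees the cheaper description.

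**Design 1.** 70% low and 30% high risk, 4 inputs, within-group correlation 0.3, means apart by s low-group SDs on each input in alternating direction. The Mahalanobis distance on the low-group scale is √(4s²/0.7): 4.8 for s = 2 and 2.4 for s = 1. Ranges are over repeat runs with separately written code.

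| Setting | Common Σ: 3 or 4 groups |
|---|---|
| s = 2, SD ratio 2, n = 150 | 92–97% |
| s = 2, SD ratio 2, n = 105 | 70–84% |
| s = 2, SD ratio 1.5, n = 150 | 40–42% |
| s = 2, SD ratio 1.25, n = 120 | 6% |
| s = 1, SD ratio 2 | 39% |
| s = 1, SD ratio 1.5, n = 120 | 7% (one group in 54–55%) |
| s = 2, equal spread, n = 120 | about 0% (two groups in 99–100%) |

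With the covariance chosen by BIC, the first three settings gave two groups in 97–100% of runs. At n = 105 and SD ratio 2, agreement with true membership (adjusted Rand index) rose from 0.69 to 0.87. With s = 1 and SD ratio 1.5, BIC-chosen covariance found two groups in 71%. With eight inputs at that separation and ratio, the Rand index rose from 0.23 to 0.72. With equal spread, or with only one true group, the two methods gave practically the same result.

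**Design 2.** n = 120, one third high risk, independent inputs, p = 2, 4 or 6, distance D of 3 or 4 low-group SDs, 60 runs per cell. Share reporting 3 or 4 groups:

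| Variance ratio (SD ratio) | Common Σ | BIC-chosen |
|---|---|---|
| 1 (1) | 0–2% | 0–2% |
| 2 (1.4) | 3–30% | 0–5% |
| 4 (2) | 48–92% | 0–3% |
| 9 (3) | 88–100% | 0–3% |

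Under-detection also appears here. At p = 6, D = 3 and variance ratio 2, a common Σ gave one group in 63% and two in 32%; BIC-chosen covariance gave two in 83%. At the same p and D with equal variances, both methods gave one group in 87%, so that loss does not come from the covariance assumption.

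**Would a diagnostic catch it?** Take the over-split runs, hold K fixed, and compare common with unequal covariance by BIC. At p = 4 and D = 4 this flagged 44% at variance ratio 2, 88% at ratio 3 and 95% at ratio 4. In the first three settings of design 1 it flagged 97%, 92% and 83%.

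**Monte Carlo error.** At most √(0.25/R) for R runs: 8 points at 40, 6.5 at 60, 5 at 100, 4 at 150. Two runs of the cell p = 4, D = 4, variance ratio 2 gave 25% (60 runs) and 12% (150 runs) over-splitting, so the ratio-2 figures are rough.

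**The case against.** A common Σ is a defensible, parsimonious choice, and the plan gives a reason for it: feasible estimation. With 10 inputs and three groups it needs 2 + 30 + 55 = 87 parameters, against 2 + 30 + 165 = 197 for group-specific matrices, from at most 150 subjects. The remark about BIC describes general practice; it is not a rule that this plan breaks. This stands, and it is why the fix should not impose unrestricted matrices.

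A reader might infer that Aim 1 will split its high-risk group and report three or four groups where there are two. The documents do not support that. They give no variances, separations, group sizes or variable count, and do not say that the high-risk group is the more variable one. The highest percentages need an SD ratio near 2, and design 1 at s = 2 has almost disjoint groups.

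A reader might also infer that the planned diagnostics cannot see the problem because the cut pieces look more alike. In the common-Σ clusters a true variance ratio of 4 did shrink to a median of about 2.4, but that is still visible, and the same-K comparison flagged most large-ratio cases. What remains is that the plan does not commit to that comparison, that it is weaker at modest ratios, and that a flag has no stated consequence for K.

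**Conclusion.** The point holds conditionally. The plan fixes a common Σ in advance and leaves the check and the fallback open. If the groups differ in spread, the number of groups can be wrong in either direction:

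- Well-separated groups: over-splitting in about 70–95% of simulated trials at SD ratio 2 (n = 105 to 150), and about 40% at SD ratio 1.5 (n = 150).
- Moderate separation and SD ratio 1.5: over-splitting in about 7%; missing the groups is more common.
- Equal spread: no loss from a common Σ.

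These figures rest on the assumed SD ratios and separations, two normal groups, K chosen by BIC and no variable selection. The case for a change does not depend on any one of those settings: BIC-chosen covariance matched or improved on a common Σ in the normal-group settings tried, apart from Monte Carlo error. This is a cheap improvement to the plan, not a demonstrated error in it.

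**What to change.** In the Aim 1 analysis plan, replace the sentence that pre-sets a common Σ with wording such as:

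*For each K in a stated range, we will fit a common Σ, a common shape with group-specific volume, and group-specific Σ_k. The last will be fitted only where group sizes support stable estimation, with a guard against near-singular solutions. K and the covariance structure will be chosen jointly by BIC. The common-Σ solution will be reported as a sensitivity analysis.*

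A common Σ stays in the candidate set, so the feasibility argument is kept and BIC can still select it. If the sponsor prefers to keep a common Σ as the main model, the least that is needed is to name the diagnostic and its threshold and to say how K is chosen again if it fails.

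The cost is one passage of text and a few extra fits on the same data. The downside is a slightly larger model search and more parameters where Σ_k is unrestricted, which BIC penalises.
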